9.3. Scheduled Follow-up Visit Windows

Data analyses include follow-up visits, regardless of whether the visit occurs within the window. Therefore, a late visit is preferred over a missed visit but must be accompanied by a deviation report. Follow-up visit windows are listed in [Table 4](#). Should a subject miss a visit or the visit falls outside the pre-specified window, a study deviation must be reported and the original follow-up schedule maintained for subsequent visits.

Table 4: Visit Windows

Visit	Visit ranges
LFP Screening	1-45 days after enrollment
cDBS Baseline	30-45 days after LFP Screening
aDBS Setup	1-45 days after Baseline
aDBS Adjustment	0-60 days after aDBS setup complete
Randomization / Day 0	No greater than 60 days after aDBS setup complete
aDBS Evaluation Visit 1	30-45 days after Day 0
aDBS Evaluation Visit 2*	30-45 days after Evaluation visit 1
Visit 3	45-60 days after Evaluation Visit 2 (or Evaluation Visit 1 if the subject is only configured to one aDBS mode)
Visit 4	45-60 days after Visit 3
Visit 5	90 +/- 14 days after Visit 4
Visit 6	90 +/- 14 days after Visit 5
Extended Access Visits	Every 180 +/- 60 days beginning after Visit 6 and every 6 months thereafter following the previous extended access visit

* If two aDBS modes are set up

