9.5. Prior and Concomitant Medications

All concomitant medications, except for over-the-counter medications and herbal supplements, will be collected for this study. All Parkinson's disease medications will be collected for this study. Subjects' Parkinson's disease medication must be stable at the time of enrollment in the trial through the end of the aDBS Evaluation Phase. During this time, the investigator should make only clinically necessary changes to PD medication.

There are no medication restrictions in the study unless they are investigational and may confound the study results, in which case, prior approval would be needed from Medtronic.

Parkinson's disease medications will be held prior to the LFP Screening and aDBS Setup visits. See [Table 5: PD Medication Off/On Definitions](#).

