9.8.1. LFP Screening Visit

1-45 days after Enrollment

The subject will arrive for the visit off PD medication and on cDBS. Confirm the subject’s PD medication was appropriately withheld as specified in [Table 5](#). If the subject’s PD medications were not appropriately withheld, consider rescheduling the study visit.

Table 5: PD Medication Off/On Definitions

Term	Definition
Off PD Medication	Subject stops taking PD medication(s) for the following time periods prior to a study visit: 
• 72 hours extended-release forms of dopamine agonists• 24 hours regular form of dopamine agonists, controlled release forms of carbidopa/levodopa

Medtronic Business Restricted

	
12 hours regular carbidopa/levodopa, entacapone, rasagiline, selegiline, amantadine
On PD Medication	Optimal motor response to PD medication (“best” On). The clinical symptoms should be stable for at least 10 minutes and both, patient and investigator should agree that the best On of the patient has been reached.
Current PD Medication(s)	Medication the subject is taking for treatment of PD on the day prior to initiating the hold requirements for the Off medication state

Data will be collected, including the following:

- MDS-UPDRS III (Off stim/Off med)
- BrainSense setup and Signal test
- Concomitant medications
- Time of last dose of PD medications taken prior to the visit
- Programming session upload to Medtronic via CDU, with BrainSense data included in the JSON session data report
- Adverse Event and device deficiency assessment

At the start of the visit, the clinician will turn off the subject’s cDBS for approximately 15 minutes.

Following this DBS washout, the trained rater will conduct the MDS-UPDRS III Off med/Off stim assessment.

Next, the clinician should follow the BrainSense setup workflow and perform a Signal Test, using the commercially available Clinician Programmer System, to assess LFP the screening inclusion criterion. The subject must have Alpha - Beta band amplitude $\geq 1.2 \mu\text{Vp}$ detected on at least one (left or right) DBS lead on sensing channels 0-2, 0-3, or 1-3; 8-10, 8-11, or 9-11.

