If the subject does not meet all of the LFP screening inclusion criteria and/or meets the LFP screening exclusion criterion, they will be exited from the study following the process in [Section 9.19](#), including a programming session upload to Medtronic via CDU. No further study-related procedures will be completed, and subjects will be followed according to the center’s standard procedures.

At the end of the visit, the programming session, with BrainSense data included in the JSON session data report, will be uploaded to Medtronic via CDU. The subject may resume taking their normal PD medication.

The subject will be reminded of the use of the PD Home Diary and the use of the PKG Watch.

The subject will leave the visit on their current cDBS settings with BrainSense set to Passive Sensing Only in all groups where BrainSense setup was utilized.

Medtronic Business Restricted

9.8.2. cDBS Baseline Period

The subject will remain on cDBS with BrainSense set to Passive Sensing Only for the duration of the period.

Prior to the scheduled cDBS Baseline visit, the PKG Watch will be given to the subject or mailed to the subject's home. Upon receipt, the subject will put on and activate the PKG Watch. The PKG Watch will be worn on the most affected side for at least 6 consecutive days in the 14 days prior to the scheduled cDBS Baseline visit. After the recording, the subject will return the PKG Watch in the pre-paid mailer or bring it to the site for return at the visit.

The PD Home Diary will also be provided to the subject in advance of the visit and will be completed for at least 3 consecutive days in the 14 days prior to the scheduled cDBS Baseline visit. If possible, the PD Home Diary will be completed at the same time as the PKG Watch is worn.

Some assessments may be completed prior to each scheduled visit. See [Section 9.15](#) for detailed information about the administration of each assessment.

Subjects should be contacted prior to the cDBS Baseline Visit to remind them to complete the required between-visit activities (PKG Watch, PD Home Diary and assessments (if applicable)).

9.8.3. cDBS Baseline Visit

30-45 days after LFP screening

Baseline data will be collected, including the following:

- PDQ-39
- EQ-5D-5L
- VHI (worst condition)
- VHI (best condition)
- Parkinson's Disease Sleep Scale (PDSS-2)
- MDS-UPDRS I (Part A) – trained rater
- MDS-UPDRS Patient Questionnaire (Part IB and II) (best condition)

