- MDS-UPDRS Patient Questionnaire (Part IB and II) (worst condition)
- MDS-UPDRS III (On stim (cDBS)/On med) – trained rater
- MDS-UPDRS IV – trained rater
- Collect PD Home Diary and review for completeness
- Concomitant medications
- Collect PKG Watch or confirm it was returned
- AE and device deficiency assessment
- Programming session upload to Medtronic via CDU, with BrainSense data included in the JSON session data report

Medtronic Business Restricted

Following cDBS baseline data collection, the programming session, with BrainSense data included in the JSON session data report, will be uploaded to Medtronic via CDU.

9.9. aDBS Setup and Adjustment Phase

This phase consists of an aDBS Setup Visit and an optional aDBS Adjustment period and ends with randomization. Subjects will be blinded to the aDBS mode during the aDBS Setup and Adjustment Phase. If the blind is broken, document the reasons for unblinding in the subject's source documentation and report as a deviation.

9.9.1. aDBS Setup Visit

1-45 days after cDBS Baseline visit

The aDBS Setup visit may be conducted in one day or may occur over two days, with the final day being no more than 45 days following the cDBS Baseline visit. The aDBS Setup visit should be conducted on sequential days, but when non-sequential days are scheduled there must be no more than 14 days between the visit days.

The subject will arrive for the visit off PD medication and on cDBS. Confirm the subject's PD medication was appropriately withheld as specified in [Table 5](#). If the subject's PD medications were not appropriately withheld, consider rescheduling the study visit.

Data will be collected, including the following:

- Concomitant medications
- Time of last dose of PD medications taken prior to the visit
- PD medication dose given at the visit (if applicable)
- Adverse Event and device deficiency assessment

The clinician should follow the BrainSense setup workflow using the investigational Clinician Programmer System. The subject must have Alpha - Beta band amplitude $\geq 1.2 \mu\text{Vp}$ detected on at least one (left or right) DBS lead on sensing channels 0-2, 0-3, or 1-3; 8-10, 8-11, or 9-11.

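### The aDBS Setup window opens one day after cDBS Baseline whatever the drug, so a 72-hour agonist hold can start before Baseline and fall on cDBS diary days; the likely effect is small and the remedy cheap

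*Protocol*

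**What the plan says.** - **Setup window.** Table 4 (protocol 9.3) gives "1-45 days after Baseline" and 9.9.1 gives "1-45 days after cDBS Baseline visit". Neither depends on the subject's medication.
- **Medication state at Setup.** Section 9.9.1 requires the subject to arrive off medication as defined in Table 5, and 9.5 states that "Parkinson's disease medications will be held prior to the LFP Screening and aDBS Setup visits". The longest hold in Table 5 is "72 hours extended-release forms of dopamine agonists". Regular agonists and controlled-release levodopa need 24 hours; the remaining listed drugs need 12.
- **Baseline measurements.** Under 9.8.2 the cDBS diary covers "at least 3 consecutive days in the 14 days prior to the scheduled cDBS Baseline visit". The Baseline visit (9.8.3) includes an on-medication MDS-UPDRS III. For that state Table 5 asks that "patient and investigator should agree that the best On of the patient has been reached".
- **Use of the diary.** Protocol 13.4.4 and SAP 7.9.1.4 accept any complete 24-hour period from the cDBS Baseline period, on the ground that stimulation is stable. They keep up to seven periods closest to the visit and accept as few as one. Neither mentions a medication hold.
- **Evaluation visits.** Under 9.10.1 and 9.10.2 subjects attend on their normal Parkinson's medication.

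**The concern.** A site can keep to every visit window and every hold and still have a subject complete part of the cDBS diary while an extended-release agonist is withheld. The stable-medication rule in 9.5 does not prevent this, because the same section schedules the hold before Setup.

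The distortion would affect one side of the comparison only. On time lost at Baseline lowers the cDBS value, raises the aDBS minus cDBS difference, and makes the subject more likely to meet the threshold of minus one standard deviation. That probably favours aDBS. The direction is not certain, because less drug could also reduce troublesome dyskinesia and so increase the diary outcome at Baseline. The descriptive diary change in SAP 7.9.3.7 would carry the same distortion, and the on-medication MDS-UPDRS III comparison possibly part of it.

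**Working it through.** **1. The plan's own power figure.** Protocol 13.2.4 gives n = 36, a performance goal of 50%, an alternative of 85%, one-sided alpha 0.0125 and power of at least 90%. In the exact binomial at p = 0.5, P(X ≥ 26) = 0.0057 and P(X ≥ 25) = 0.0144, so the pass mark is 26 of 36 (72%). Power at 85% is 98.6%, so the stated figure holds.

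**2. How far the hold reaches back.** For a hold of L hours and Setup on day k at the same clock time as Baseline, the hours held before Baseline are max(0, L − 24k).

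| Hold | Setup day 1 | Setup day 2 | Setup day 3 |
|---|---|---|---|
| 72 h | 48 | 24 | 0 |
| 24 h | 0 | 0 | 0 |
| 12 h | 0 | 0 | 0 |

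A 72-hour hold with Setup on day 3, or a 24-hour hold with Setup on day 1, overlaps only if Setup is earlier in the day than Baseline was. A 12-hour hold does not overlap with a next-day Setup.

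**3. How often held days fall in the diary.** A run of m days has 14 − m + 1 positions in the 14-day window: 12 for m = 3 and 8 for m = 7. With two held days (Setup day 1), one position contains both, one contains a single held day, and the other 10 (m = 3) or 6 (m = 7) contain none. With one held day (Setup day 2), a single position is touched. Random placement is an assumption.

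**4. Effect on an affected subject.** These assumptions are not in the documents: a held day costs h = 1 to 4 hours of On time, the SD of the change is 2 to 4 hours, there is no true difference, and the affected subjects' influence on the SD itself is ignored. With j held days in the diary, P(meets threshold) = Φ(1 + j·h/(m·SD)). At j = 0 this is Φ(1) = 0.8413.

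- Setup day 1, highest (m = 3, h = 4, SD 2): (Φ(2.333) + Φ(1.667) + 10 × 0.8413)/12 = 0.8630.
- Setup day 1, lowest (m = 7, h = 1, SD 4): (Φ(1.071) + Φ(1.036) + 6 × 0.8413)/8 = 0.8445.
- Setup day 2, over the same ranges: 0.8424 to 0.8506.

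**5. Effect on the trial.** Assume 1 to 4 of 36 subjects are extended-release users set up that early. The shift is n × (mean − 0.8413)/36.

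- Day 1: 1 × 0.00314/36 = 0.009 points, up to 4 × 0.02164/36 = 0.240 points.
- Day 2: 0.003 to 0.103 points.
- If a held day gains 1 hour instead, day 1 gives −0.009 to −0.127 points (upper end 4 × 0.01146/36).
- Power is 97.96% at p = 0.8413 and 98.17% at p = 0.8437.

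**6. Less favourable conditions.** If all four affected subjects had both held days inside a three-day diary (h = 4, SD 2), the shift would be 4 × (Φ(2.333) − 0.8413)/36 = 1.65 points.

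A separate simulation used 20,000 trials with n = 36, normal differences, SD 3 hours and the sample SD as threshold. Diary days ended at Baseline, Setup was on day 1, and each held day lost 1 to 3 hours. Shares of 5%, 10% and 20% are 1.8, 3.6 and 7.2 of 36 subjects.

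| True mean difference | Chance of passing, no overlap | 5–10% affected | 20% affected |
|---|---|---|---|
| 0 | about 0.98 | 0.985–0.992 | 0.987–0.997 |
| −0.5 SD | 0.40 | 0.41–0.54 | 0.44–0.66 |
| −1 SD | about 0.006 | 0.007–0.016 | 0.008–0.037 |

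**The case against.** The text already works against the scenario. The Baseline motor examination must be done on medication, medication is to be stable from enrolment, and sites have up to day 45 for Setup, so running a 72-hour hold through Baseline would be an odd choice. The Version History entry for version 3.0 explains that the one-day opening was meant for subjects who take neither controlled-release levodopa nor dopamine agonists. Overlap therefore needs an extended-release user, Setup on day 1 or 2, and a diary placed late. The documents do not show that this combination occurs. The hours lost, the SD and the number affected are all assumed. Setup visits may also be largely finished by version 5.0.

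Most of this stands as a limit on size. It does not remove the gap. The on-medication requirement partly protects the rating, since a subject still taking levodopa could reach a best On state, but it does not protect a diary already filled in at home. The change log is not operative text, and its difference from the current text is not itself an error; it does show that the restriction proposed here agrees with the sponsor's stated reason.

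**Conclusion.** The concern holds as a minor design point. The timing follows directly from the current text: an extended-release agonist user set up on day 1 or 2 starts the hold about 48 or 24 hours before Baseline, and the analysis rules would accept the affected diary periods. Exposure is confined to those subjects, apart from the clock-time edge cases.

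The size is a judgement resting on the assumptions above. With no true difference and 1 to 4 of 36 subjects affected, the shift is at most about a quarter of a percentage point, and the primary conclusion is unlikely to change. The effect cannot be taken as zero. If aDBS were moderately worse than cDBS and a larger share of subjects had late diaries and early Setup visits, the chance of passing could rise noticeably. The sample size is unaffected.

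**What to change.** 1. **Window.** In Table 4 and 9.9.1, require Setup to follow Baseline by at least the subject's longest Table 5 hold, and allow no hold to start until the Baseline assessments and diary are complete. No hold length changes. This takes a footnote and one line of text. Extended-release users lose about 2 to 3 days at the early end of a 45-day window.
2. **Sensitivity analysis.** Leave the primary dataset as it is. Add to SAP 7.9.1.6 and protocol 13.4.6 an analysis that excludes cDBS diary periods overlapping a Table 5 hold, and flag affected on-medication MDS-UPDRS III ratings at Baseline. The hold can be dated from an item already collected at Setup: "Time of last dose of PD medications taken prior to the visit". This works only where last-dose times were recorded by drug, which the documents do not state. A subject whose only complete periods fall within a hold would drop out of this analysis alone.

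If all Setup visits are finished, only the second change applies. It would help to report alongside it how many extended-release users were set up on day 1 or 2.

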9.9.3. Randomization

Day 0 (no greater than 60 days after aDBS setup complete)

Randomization may occur at the aDBS setup visit, at an unscheduled visit during the aDBS Adjustment Period, or as a standalone visit. All subjects for whom aDBS was set up will complete this visit.

The investigator will assess each aDBS mode that was set up utilizing the aDBS Global Impression of Change (GIC) provided in [Appendix A - aDBS Global Impression of Change Score \(GIC\)](#). Efficacy and side effects are assessed on a scale from 1 to 21. The lower the score the better the efficacy and the less side effects. A score of 8 or less indicates the aDBS mode is acceptable. The investigator will also ensure that the subject is comfortable remaining in the aDBS mode(s) for the duration of the trial.

If only one aDBS mode was set up for a subject, they will not be randomized, but the physician should still complete the aDBS GIC and data collection for the visit.

Data will be collected, including the following:

- Concomitant medications
- GIC value for each aDBS mode that was set up
- Adverse Event and device deficiency assessment

For subjects in whom both aDBS modes are acceptable as compared to cDBS (using the aDBS GIC), unblinded site personnel will obtain the randomization assignment via Remote Data Capture (RDC). The randomization assignment can be obtained upon completion of the aDBS GIC and randomization CRFs.

Randomization will occur to one of two possible treatment sequences if both aDBS modes are acceptable as compared to cDBS (using the aDBS GIC) (dual threshold mode followed by single threshold mode or vice versa) and will be stratified by target site location (STN/GPi). The two sequences will be randomly permuted in blocks of two and four. If an aDBS mode is unacceptable as compared to cDBS (using the aDBS GIC), that subject will be assigned the mode which was acceptable. The randomization schedule will be prepared by Medtronic and it will be maintained at Medtronic. Subjects will continue to be blinded to the aDBS mode during the aDBS Evaluation Phase. If the blind is broken, document the reasons for unblinding in the subject's source documentation and report as a deviation.

Following randomization, the clinician will program one group to the randomized aDBS mode.

Subjects for whom one aDBS mode is unacceptable as compared to cDBS (using the aDBS GIC) or for whom only one mode could be acceptably configured will not be randomized and will complete one aDBS evaluation visit in the aDBS mode that was acceptable to the subject.

In order to blind the subject to the aDBS mode assigned, the clinician will set the group name of the aDBS mode being evaluated during each period to "aDBS," and the group name of the mode not being evaluated to "Do not use" on the Clinician Programmer. These group names will be displayed on the Patient Programmer.

Medtronic Business Restricted

If neither aDBS mode is acceptable to the subject, the subject will be exited from the study following the process in [Section 9.19](#). No further study-related procedures will be completed, and the subject will be followed according to the center's standard procedures.

If randomization is conducted as a separate visit, the programming session, with BrainSense data included in the JSON session data report, will be uploaded to Medtronic via CDU.

The subject will be instructed on the use of the PKG Watch and PD Home Diary in the aDBS Evaluation Phase.

9.10. aDBS Evaluation Phase

This phase consists of up to two treatment periods; one per acceptable aDBS mode. After each treatment period, there is an aDBS evaluation visit. The subject's PD medications will remain stable from enrollment through the end of the aDBS Evaluation Phase, unless changes are clinically necessary.

During the aDBS Evaluation Phase, the subject may return to the study center for further aDBS adjustment in each randomized aDBS mode. All adjustments must be completed at least 14 days prior to the evaluation visit for that mode. Any adjustments will be recorded as unscheduled visits. Any adjustments during the 14 days prior to the evaluation visit will be considered a protocol deviation.

Prior to each scheduled aDBS Evaluation visit, the PKG Watch will be given to the subject or mailed to the subject's home. Upon receipt, the subject will put on and activate the PKG Watch. The PKG Watch will be worn on the most affected side for at least 6 consecutive days. After the recording, the subject will return the PKG Watch in the pre-paid mailer or bring it to the site for return at the visit. The subject will also be provided with the PD Home Diary in advance of the visit and will complete it for at least 3 consecutive days in the 14 days prior to each scheduled aDBS Evaluation Visit. If possible, the PD Home Diary will be completed at the same time as the PKG Watch is worn.

Some assessments may be completed prior to each scheduled visit. See [Section 9.15](#) for detailed information about the administration of each assessment.

Subjects should be contacted prior to each aDBS Evaluation Visit to remind them to complete the required between-visit activities (PKG Watch, PD Home Diary and assessments (if applicable)).

9.10.1. Evaluation Visit 1

30-45 days after randomization

The subject will arrive for the visit on their normal PD medications and on aDBS.

The clinician will confirm the subject is in the assigned mode for the visit. If the subject is not in aDBS, the clinician will program the subject to the assigned aDBS mode and all On stim assessments will be

Medtronic Business Restricted

performed in the assigned mode. If the subject completed the evaluation period in the incorrect aDBS mode, all On stim assessments will be performed in the incorrect aDBS mode.

The following data will be collected:

- PDQ-39
- EQ-5D-5L
- C-SSRS
- MDS-UPDRS I (Part A) – trained rater
- MDS-UPDRS Patient Questionnaire (Part IB and II) (best condition)
- MDS-UPDRS Patient Questionnaire (Part IB and II) (worst condition)
- MDS-UPDRS III (On stim (aDBS)/On med) – trained rater
- MDS-UPDRS IV – trained rater
- VHI (worst condition)
- VHI (best condition)
- PDSS-2
- Patient preference questionnaire
- Collect PD Home Diary and review for completeness
- Concomitant medications
- Collect PKG Watch or confirm it was returned via mail
- Adverse Event and device deficiency assessment

At the end of the visit, the programming session, with BrainSense data included in the JSON session data report, will be uploaded to Medtronic via CDU.

Next, the clinician will program the subject to the other assigned aDBS mode and label that group “aDBS.” The group for the aDBS mode the subject just completed evaluation of will be re-labeled “Do not use” on the Patient Programmer.

The subject should be reminded that they will receive the PKG Watch prior to the aDBS Evaluation Visit 2 and will put on and activate the PKG Watch upon receipt. The subject will wear the PKG Watch for at least 6 consecutive days in the 14 days prior to the scheduled aDBS Evaluation Visit 2. After the recording, the subject will return the PKG Watch in the pre-paid mailer or bring it to the site for return at the visit. The subject will also be reminded that they will be provided with the PD Home Diary in advance of the visit and will complete it for at least 3 consecutive days in the 14 days prior to the next aDBS Evaluation Visit.

If only one aDBS mode is being evaluated, the subject will continue into the Long-term Follow-up phase and skip aDBS Evaluation Visit 2.

9.10.2. Evaluation Visit 2

If two aDBS modes are being assessed

30-45 days after Evaluation visit 1

Medtronic Business Restricted

The subject will arrive for the visit on their normal PD medications and on aDBS.

The clinician will confirm the subject is in the assigned mode for this visit. If the subject is not in aDBS, the clinician will program the subject to the assigned aDBS mode and all On stim assessments will be performed in the assigned mode. If the subject completed the evaluation period in the incorrect aDBS mode, all On stim assessments will be performed in the incorrect aDBS mode.

The following data will be collected:

- PDQ-39
- EQ-5D-5L
- C-SSRS
- MDS-UPDRS I (Part A) – trained rater
- MDS-UPDRS Patient Questionnaire (Part IB and II) (best condition)
- MDS-UPDRS Patient Questionnaire (Part IB and II) (worst condition)
- MDS-UPDRS III (On stim (aDBS)/On med) – trained rater
- MDS-UPDRS IV – trained rater
- VHI (worst condition)
- VHI (best condition)
- PDSS-2
- Patient preference questionnaire
- Collect PD Home Diary and review for completeness
- Concomitant medications
- Patient and physician preferred aDBS mode and reason for selecting preferred mode (at end of visit)
- Collect PKG Watch or confirm it was returned via mail
- Adverse Event and device deficiency assessment

At the end of the visit, the programming session, with BrainSense data included in the JSON session data report, will be uploaded to Medtronic via CDU.

Following the final aDBS visit, the clinician will program the subject to the chosen DBS mode (clinician & patient preference) for the long-term follow-up phase and record the reason for selecting that mode.

If the chosen DBS mode is cDBS, the subject will be exited from the study following the process in [Section 9.19](#). No further study-related procedures will be completed, and the subject will be followed according to the center's standard procedures.

The subject should be reminded that they will receive the PKG Watch prior to the next visit and will put on and activate the PKG Watch upon receipt. The subject will wear the PKG Watch on the most affected side for at least 6 consecutive days in the 14 days prior to the scheduled visit.

